Information gathered in the post-treatment qualitative interview will be analyzed to identify participants' thoughts about the usefulness of Altitudes as well as feedback to improve the intervention for others. Qualitative analysis will be conducted on the feedback interviews using grounded theory. As with qualitative analysis, a codebook will be developed by the research team in which thematic analysis of all interviews will conducted. The codebook will include themes and subthemes with a focus on the different perceived strengths of the intervention as well as areas that need improvement.

Secondary Outcomes: The platform will collect information about frequency of engagement with Altitudes (i.e., site usage). Psychosocial outcomes will be summarized within and between conditions using univariate statistics (e.g., means, standard deviations). To evaluate change over time on psychosocial outcomes, we will utilize linear mixed models (LMM) including fixed effects of time, group, and group x time interactions and random effects at the participant level. We will calculate changes from baseline at each time point using least-squares means and standardized least-squares mean differences to estimate within- and between-group changes, respectively. To estimate magnitude of change from baseline, we will calculate effect sizes. We will explore the relationship between baseline characteristics (e.g., age, gender) and engagement data (i.e., site usage information) on any changes in psychosocial outcome measures from baseline to midpoint and posttreatment using multiple linear regression. We will use Pearsons correlation coefficients to examine associations between carers' involvement in Altitudes and their loved one with FEP's use of emergency services (e.g., ED visits). If possible based on sample size, we will dichotomize engagement data (site usage) between low engagement and high engagement before comparing site usage with emergency service utilization.

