As this platform will be provided as an adjunct to CSC clinical care, pertinent clinical impressions and other relevant clinical information will be shared with the individual's clinical team at their respective FEP clinic.

All individual interviews will be conducted virtually via secure Zoom and will be led by the Altitudes study coordinator and/or a graduate student in clinical psychology at UNC-Chapel Hill. All feedback sessions will be digitally recorded, and will be de-identified and transcribed by a member of the research team or a transcription service. The purpose of these recordings and transcriptions is to allow the research team to examine the feedback provided in the interviews for the purposes of improving the platform to better support families and caregivers in supporting their loved ones experiencing psychosis via psychoeducation and skills such as healthy coping mechanisms.

Subjects

Up to 30 total Altitudes participants will be recruited from two of the FEP clinics in North Carolina (OASIS & SHORE) as it is a pilot study, specifically family members of individuals experiencing FEP. An additional 30 control participants will be recruited from three other FEP clinics in North Carolina (Eagle, Encompass, and AEGIS). All participants will have a loved one currently enrolled in or recently graduated from a CSC program. Demographic and clinical information that will be collected as self-report for possible use as covariates includes: 1) participant demographics: age, sex/gender identity, race/ethnicity, level of education, current zip code, relationship to loved one, employment status, proximity to the loved one with psychosis (e.g., cohabitating, living in different states), hours of contact with loved one per week on average, number and ages of any other children; and 2) young person with psychosis' demographics and relevant clinical information: age, sex/gender identity, level of education, stage of recovery, and level of education.

Eligibility Criteria

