1. Descriptive statistics examining Site Usage Information [Time Frame: Duration of the trial, from onboarding at baseline through post-treatment]

The Altitudes platform passively collects engagement data, including the number of therapeutic pathways started and completed as well as any posts or comments made on the platform. We will provide mean and standard deviation scores for each site usage category, as well as a range, for the Altitudes group only. Depending on sample size, we will categorize users in low or high engagement groups.

2. Mean Change in UCLA Loneliness Scale Score [Time Frame: Baseline, Post-treatment, up to 14 weeks]

The UCLA Loneliness scale is a 20-item scale. Answers are on a 4-point scale with options "I often feel this way," "I sometimes feel this way," "I rarely feel this way," and "I never feel this way." Possible scores range from 20 to 80. Higher scores reflect worse outcomes (greater feelings of loneliness). The UCLA Loneliness Scale is a part of the PhenX Toolkit.

3. Mean Change in Multidimensional Scale of Perceived Social Support - total score [Time Frame: Baseline, Post-treatment, up to 14 weeks]; Alternative form for Altitudes participants, original form for control group.

The MOS Social Support Survey is a 16-item scale. Answers are on a 7-point scale with options ranging from "very strongly disagree" to "very strongly agree". Possible scores range from 16 to 112. Higher scores reflect higher feelings of social support (more perceived social support).

4. Mean Change in the Experience of Caregiving (ECI) Score [Time Frame: Baseline, Post-treatment, up to 14 weeks]

The Experience of Caregiving (ECI) Scale is a 66-item scale. Answers are on a 5-point scale starting at 0 with options "never," "rarely," "sometimes," "often," and "nearly always". Possible scores range from 0 to 264. Higher scores indicate greater feelings of preparedness for caregiving whereas lower scores reflect feeling less prepared to provide caregiving.

5. Mean Change in Family Questionnaire of Expressed Emotion - Total Score [Time Frame: Baseline, Post-treatment, up to 14 weeks]. The Family Questionnaire of Expressed Emotion is a part of the PhenX Toolkit.

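### The association between platform usage and emergency service use may be tested on a low/high split with no stated cut-off; a rank correlation on the full usage scale would serve better than either the split or raw Pearson

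*Combined protocol and SAP*

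**What the plan says.** In the Protocol Synopsis, Statistical and Analytic Plan, Secondary Outcomes, two consecutive sentences deal with emergency service use. The first is unconditional: "We will use Pearsons correlation coefficients to examine associations between carers' involvement in Altitudes and their loved one with FEP's use of emergency services". The second is conditional: "If possible based on sample size, we will dichotomize engagement data (site usage) between low engagement and high engagement before comparing site usage with emergency" use.

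The Data Analytic Plan, Secondary Outcome Measures, item 1, returns to the grouping: "Depending on sample size, we will categorize users in low or high engagement groups". The same item promises descriptive summaries: "We will provide mean and standard deviation scores for each site usage category, as well as a range, for the Altitudes group only". It describes the usage data as the "number of therapeutic pathways started and completed as well as any posts or comments made on the platform".

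Neither section gives a cut-off, a rule for choosing one, the sample size that would trigger the split, or a single usage index. Neither says whether the low/high comparison takes the place of the Pearson correlation or sits beside it.

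Usage against psychosocial change is a separate analysis, described as relating "engagement data (i.e., site usage information) on any changes in psychosocial outcome measures from baseline to midpoint and posttreatment using multiple linear regression". No split is mentioned for it.

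The number with usage data is capped under Research Design & Methods, Subjects: "Up to 30 total Altitudes participants will be recruited from two of the FEP clinics in North Carolina".

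**The concern.** Usage is recorded as counts. Cutting it in two treats carers just either side of the line as opposites and treats everyone on one side as alike. In a group of at most 30 that is an expensive loss. The condition also runs the wrong way, since a larger sample gives no reason to discard the scale.

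An unstated cut-off is a second weakness, because the apparent association can depend on where the line falls. The pilot is meant to inform later trials, so a weakened or cut-dependent association between usage and emergency visits could be carried into their design.

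The fallback matters too. Usage counts and emergency visits are both likely to be skewed, and Pearson on raw skewed counts is fragile. Deleting the split and leaving Pearson would not settle the matter.

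**Working it through.** **Plan's own figure.** There is none to reproduce. The Power Analysis section reports no power calculation, and no expected correlation or cut-off is given.

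**Inputs.** From the documents: at most 30 carers with usage data, Altitudes arm only; several usage counts; a conditional low/high split without a cut-off. Assumed: two-sided 5% level, true correlation 0.3 to 0.5, and n = 30 or n = 24 (30 × 0.8, a 20% loss).

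**Step 1: information kept by a split.** For normal usage cut at quantile q and a linear relation, the share retained is φ(z_q)² / [q(1 − q)]. At the median this is (1/2π) / 0.25 = 2/π = 0.637.

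- Loss: 1 − 0.637 = 36%.
- Correlation multiplied by √0.637 = 0.798.
- Effective sample: 30 × 0.637 = 19.1.

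Uneven cuts of normal usage lose more: 42% at 70/30, 46% at 75/25, 51% at 80/20, 66% at 90/10.

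If the outcome is linear in raw usage, a median split loses:

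| Usage distribution | Loss |
|---|---|
| Uniform | 25% |
| Log-normal, σ = 0.5 | 48% |
| Exponential | 52% |
| Negative binomial, k = 0.8, mean 20 | 55% |
| Log-normal, σ = 1 | 73% |

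For the four skewed shapes, a cut at the upper quarter loses 36% to 56%, which is less than their median cut.

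**Step 2: power if both variables were normal.** Power ≈ Φ(atanh(r)·√(n − 3) − 1.96). For n = 30 and r = 0.5: atanh(0.5) × √27 = 0.549 × 5.196 = 2.854, and Φ(0.894) = 81%. After a median split r becomes 0.5 × 0.798 = 0.399, so 0.422 × 5.196 = 2.195 and Φ(0.235) = 59%.

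| n | r | Full scale | Median split |
|---|---|---|---|
| 30 | 0.3 | 36.3% | 24.5% |
| 30 | 0.4 | 59.5% | 40.5% |
| 30 | 0.5 | 81.4% | 59.3% |
| 24 | 0.3 | 29.4% | 20.1% |
| 24 | 0.4 | 49.3% | 32.9% |
| 24 | 0.5 | 71.1% | 49.0% |

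Simulation with 40,000 runs agreed to within about 2 percentage points. The true correlation detectable with 80% power at n = 30 is 0.49 on the full scale and 0.492 / 0.798 = 0.62 after the split.

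**Step 3: power with an outcome more like emergency visits.** Visits are events, so the table above is optimistic. Simulations used n = 30, an assumed latent correlation of 0.5, and 20–30% of loved ones with any visit:

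- Spearman: about 46–59%.
- Median split: about 29–40%.
- Pearson on raw log-normal usage, protective association: about 8–20%, below the split.

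With normal usage and 30% having any visit, Pearson reached 59%, Spearman 57% and the split 40%. Pearson's weakness here therefore comes from raw skewed usage. When the association is protective, visits fall among light users, who are bunched at one end of a scale whose variance is set by a few heavy users.

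**Step 4: an open cut-off.** With no true association at n = 30, a fixed median cut gave about 5% false positives. The best of three cuts (lower third, median, upper third) gave 12%, and the best of any cut between roughly 20% and 80% gave 27%. With a skewed count outcome (assumed mean 0.5 visits) the figures were 4%, 11% and 25%. These show what an unrestrained search would do. The plan describes no such search.

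**The case against.** The strongest reply is that a full-scale analysis is already planned. The Pearson sentence comes first and carries no condition, so the low/high comparison may be a supplement for readers who want two groups, and then nothing is discarded. That reading is as open as replacement. Putting the split before the comparison leans towards replacement but does not settle it. What stands is the ambiguity.

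A reader might infer several stronger things that the documents do not support:

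- That the split will certainly happen. Both mentions make it conditional on sample size.
- That the trial's usage–outcome analysis as a whole is affected. The psychosocial regression has no stated split, and emergency service use is not among the numbered secondary outcome measures.
- That the cut-off will be chosen after outcomes are seen. Dependence on sample size is dependence on enrolment. The plan is silent on when the line is fixed, and that silence is all that can be claimed.
- That splitting always weakens the planned analysis. Against raw Pearson with log-normal usage and a protective association, the split does better. The gain comes from the rank method.

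It is also fair to say that this is an unpowered pilot with feasibility and acceptability as its primary aim, and that power is poor either way at r = 0.3 (36% against 25%). That limits the stakes, but it is no reason to keep an analysis that a one-sentence change improves.

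**Conclusion.** The point holds for the emergency-service association only. The plan leaves unclear whether a low/high split replaces the correlation, and it fixes no cut-off. If the split carries the inference, the loss is 36% for a median split of normal usage, more for uneven cuts of normal usage or a median cut of the skewed shapes tried, and 25% for uniform usage. With a skewed visit count and a latent correlation of 0.5, a rank correlation has about 46–59% power against 29–40% after a median split. Raw Pearson is not a safe alternative, at 8–20% in the unfavourable case.

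The level, correlations, visit rates and usage distributions are all assumptions. The calculations treat carers as independent, although more than one carer per family may enrol, so the number of distinct emergency-use outcomes could be below 30. No trial decision is stated to rest on this result, so this is a modest but cheap improvement.

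**What to change.** In the synopsis, Statistical and Analytic Plan, Secondary Outcomes, replace the Pearson sentence and the dichotomisation sentence with one statement: the association between usage, on its full scale, and emergency service use will be estimated by a Spearman rank correlation in the Altitudes group, whatever the sample size. State there and in Secondary Outcome Measures, item 1, that any low/high grouping is descriptive only. Naming the usage index in the same sentence would remove a further free choice.

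The change needs no new data. It gives up an inferential two-group contrast, and a rank coefficient is slightly less powerful than Pearson if both variables turn out near normal (at r = 0.5 and n = 30, simulated power about 77–78% against 83%).

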Expert Moderation. Family peer support workers, providers with significant experience in the psychosocial treatment, as well as graduate students with relevant clinical/research experience with FEP will serve as expert moderators. Their role is to provide guidance, monitor participants' status and ensure the safety of the social networking environment. The moderator reviews interactivity in the social networking space and information from individual participants' modules to monitor risk. The Altitudes Moderation Checklist will be completed by each moderator every time he/she/they moderates the platform. The checklist is designed to ensure moderators complete the appropriate safety checks during the moderation session, and to give moderators ideas as to how to engage users.

Treatment period. At the mid-treatment assessment period (approximately 10-14 weeks after an Altitudes participant is onboarded to the platform), clients will meet with the study coordinator over secure video conferencing. The study coordinator will use screen sharing to complete all assessment measures with the individual. Control participants will also meet via secure video conferencing with research staff approximately 10-14 weeks after their initial battery assessment.

After Altitudes participants have engaged with the platform for 24 weeks, they will be provided with an optional feedback form as a way of better understanding their experience with the platform and collecting suggestions for improving the site. Additionally, we will conduct individual feedback interviews (lasting approximately 45 minutes) with parents and caregivers. These interviews will address participants' social relationships, experiences with loneliness, and thoughts about connecting with others through Altitudes. Control participants will also complete the same measure battery via video conferencing at approximately 24 weeks after their initial survey visit.

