To evaluate the extent to which engagement in Altitudes may have impacted treatment participants' psychological health and perceptions of their social environment in comparison to the control group, all individuals will be asked to complete a battery of psychological measures at baseline, mid-treatment, and post-treatment visits. All measures will be administered by a member of the study team via secure Zoom. They will additionally complete a brief engagement measures on services they are accessing (e.g., services through the CSC program, individual therapy, group therapy at an outside organization, etc.).

At each of the three timepoints, all participants will be asked to complete the Experience of Caregiving Inventory (ECI; Szmukler), the Family Questionnaire of Expressed Emotion (Wiedemann et al., 2002), Brief COPE (Carver, 1997), UCLA Loneliness Scale (Russell, 1996), Multidimensional Scale of Perceived Social Support (For control and Alternative form for Altitudes condition; Zimet et al., 1990), Modified Psychosis Attitudes Survey (PAS; Kopelovich et al., 2022), PTSD Checklist for DSM-5 (PCL-5, Weathers et al., 2013), Post Traumatic Growth Inventory (PTGI, Tedeschi & Calhoun, 1996), General Health Questionnaire-12 (GHQ-12; Goldberg, 1972), Self-Compassion Scale – Short Form (SCS-SF; Raes et al., 2011), and Five Facet Mindfulness Scale (FFMQ; Bohlmeijer et al., 2011).

At baseline, all participants will be asked to complete a brief demographic questionnaire and answer a small number of clinical questions about their loved one (e.g., "Of the options provided below, what stage of recovery best describes your loved one?").

At midpoint, Altitudes condition participants will also be asked to provide their perceptions of the Altitudes platform and clinical moderators via four brief questionnaires: the Altitudes Health Care Climate Questionnaire (A-HCCQ), Altitudes Usability Questionnaire (AUQ), and Altitudes Perceived Competence Scale (A-PCS) and Working Alliance Inventory for guided Internet interventions (WAI-I, Gomez Penedo et al., 2019).

At posttreatment, Altitudes condition participants will be asked to participate in a qualitative interview focusing on the experience of Altitudes and deeper understanding of acceptability and feasibility of the platform.

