With approval from the IRB & clinic directors, the research time will post flyers with a description of the study and eligibility criteria in the clinic waiting rooms to allow for caregivers to self-refer and/or to enable clients with FEP to share information about the study with their loved ones. If individuals self-refer (in response to flyers), the RA and PI will consult with the treatment team first before screening the individual (i.e., to confirm their loved one is currently receiving or recently graduated from the CSC program).

Baseline Procedures

The study coordinator will meet virtually with prospective participants for about 1 hour to complete all baseline measures. The demographic form will be completed first, which collects basic information about sex, age, ancestry, education, current zip code, and basic information on their loved one, including their loved one age, duration of illness, and length of time in the CSC program. After completing these documents, the study coordinator will guide participants through virtual copies of the demographic questions and psychological measures, including the Experience of Caregiving Inventory (ECI; Szmukler), the Family Questionnaire of Expressed Emotion (Wiedemann et al., 2002), Brief COPE (Carver, 1997), UCLA Loneliness Scale (Russell, 1996), Multidimensional Scale of Perceived Social Support (For control and Alternative form for Altitudes condition; Zimet et al., 1990), Modified Psychosis Attitudes Survey (PAS; Kopelovich et al., 2022), PTSD Checklist for DSM-5 (PCL-5, Weathers et al., 2013), Post Traumatic Growth Inventory (PTGI, Tedeschi & Calhoun, 1996), General Health Questionnaire-12 (GHQ-12; Goldberg, 1972), Self-Compassion Scale - Short Form (SCS-SF; Raes et al., 2011), and Five Facet Mindfulness Scale (FFMQ; Bohlmeijer et al., 2011). Additionally, all participants will complete a brief survey on engagement with services within the CSC program and outside the program (e.g., individual therapy, family groups outside of CSC, etc.).

For Altitudes participants only, once all baseline study measures are complete, the study coordinator will conduct a 20- to 30-minute orientation of the Altitudes platform, including creation of an Altitudes profile and orientation to the features of the site. All participants will be compensated \$20.00/hour prorated to the nearest half hour for completion of this visit and their time.

Intervention Period Procedures

Mid-Treatment Procedures

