The study coordinator will meet virtually with family and support participants for approximately 1-1.5 hours to complete the post-treatment measures; however, visits for control participants is likely to be closer to a half hour. All participants will complete virtual copies of the Experience of Caregiving Inventory (ECI; Szmukler), the Family Questionnaire of Expressed Emotion (Wiedemann et al., 2002), Brief COPE (Carver, 1997), UCLA Loneliness Scale (Russell, 1996), Multidimensional Scale of Perceived Social Support (For control and Alternative form for Altitudes condition; Zimet et al., 1990). Modified Psychosis Attitudes Survey (PAS; Kopelovich et al., 2022), PTSD Checklist for DSM-5 (PCL-5, Weathers et al., 2013), Post Traumatic Growth Inventory (PTGI, Tedeschi & Calhoun, 1996), General Health Questionnaire-12 (GHQ-12; Goldberg, 1972), Self-Compassion Scale – Short Form (SCS-SF; Raes et al., 2011), and Five Facet Mindfulness Scale (FFMQ; Bohlmeijer et al., 2011). Additionally, all participants will complete a brief survey on engagement with services within the CSC program and outside the program (e.g., individual therapy, family groups outside of CSC, etc.). After completing these virtual measures, the study coordinator will lead Altitudes participants only through a feedback survey and individual feedback interview regarding the Altitudes platform, their online therapist, the Family PSS, and the community newsfeed. Altitudes participants will be welcomed to share their opinions regarding their experience, including suggestions for how to improve Altitudes in the future. All participants will be compensated \$20.00/hour prorated to the nearest half hour for completion of this visit and their time.

DATA ANALYTIC PLAN

Primary Outcome Measures*

- *Primary outcomes solely apply to those in the Altitudes condition
 - 1. Qualitative Summaries of Participant Experience in Post-Treatment Feedback [Time Frame: up to 6 months]
 - This qualitative data will be collected post-treatment from Altitudes participants. Individual interviews will discuss usage of the platform and any feedback participants may have. Feedback from participants will be summarized to include

common themes regarding likes and dislikes of the platform, implementation within the clinical setting, and participant ideas for future directions.

2. Quantitative Summaries of Participant Experience in Post-Treatment Feedback [Time Frame: up to 6 months]

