A member of the research team will meet individually with the parent or caregiver to explain the components of the Altitudes platform (or the study in general in the case of participants in the control group), elicit and answer any questions the potential participant may have after the screening then informed consent will be obtained via the DocuSign system. Altitudes participants will also create a profile on the platform and answer questions about their caregiving experience (e.g., their loved one's stage of recovery), which are introduced to each participant during the onboarding to the Altitudes platform. This data will be linked to other sources of information, including the record of their interactions within the Altitudes system (e.g., number of posts/comments in the 'Community').

The Altitudes system and data generated by users of Altitudes will be hosted on a secure web server. A range of measures are in place to ensure the security of the Altitudes website and the data generated by users. In addition, the team who developed the web application has placed measures within the application to secure the application and database against unauthorized access. These measures conform to industry best practice as defined by the Open Web Application Security Project (www.OWASP.org). All data collection visits will be conducted via secure Zoom. All interviews will also be conducted via secure Zoom and will be digitally recorded (via Zoom or using audio recorders) for the purposes of transcription. These recordings and transcripts will be immediately uploaded to a secure, password-protected server and deleted from local devices. The project electronic database (including all transcripts from interviews) will be password protected and stored securely, and will only be directly accessible by the research staff, clinicians and family peer support workers, involved in this project, or the principal investigator.

As this research program is being implemented in clinical settings, it is possible that FEP clinicians will create notes that indicate the participant is involved in the project, describe any issues that may arise, etc. that will be connected to their medical record. These documents will be stored in approved medical record systems on HIPAA-compliant computers.

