A member of the research team will meet individually with the client in order to explain the components of the study (including the Altitudes platform), elicit and answer any questions the participant may have during the screening phone call. Participants will then provide informed consent via the DocuSign platform. For Altitudes participants, it will be explained that their data will be linked to other sources of information, including the record of their interactions within the Altitudes system (e.g., number of posts/comments on the 'Community'), but the data exported from the site will be deidentified before storage on password protected drives located on secure servers. All participants will be provided with a copy of the consent form and research staff will encourage each participant to contact the principal investigator or IRB for any questions they may have related to the study or their rights as a research participant. There are also several procedures in place to ensure that prospective participants fully understand the procedures, risks, and protections of the study. First, the consent form is written in easyto-understand language. Second, participants will know the number and email of the person to call if they have any questions prior to signing the document. Participants will have the option to provide electronic consent via DocuSign's Part 11 compliant electronic consent platform (i.e., electronic signature and verification) or in person on paper with wet ink signatures if preferred.

ETHICS

Research Ethics Approval

Research ethics approval for the Altitudes Pilot will be sought from University of North Carolina at Chapel Hill's IRB.

Protocol Amendments

Any modifications to the research protocol and conduct of the study will be notified to UNC's IRB prior to their enactment. Approval from UNC's IRB will be sought for any proposed protocol amendment including changes to eligibility criteria, outcomes, analysis and changes to research personnel.

Declaration of interests

The researchers report no financial or competing interests for the conduct of the trial.

Access to Data

Personnel who will have access to one or more sources of information collected through

the course of this study include all of the listed research staff in the IRB application (all data) and the study moderators (the online data captured within the Altitudes system).

Ancillary and Post-Trial Care

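### Carers rate the platform and its moderators with study staff present, an unmitigated risk of favourable answers in rating levels and interviews, and two sections disagree on who may open transcripts

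*Combined protocol and SAP*

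**What the plan says.** **How ratings are collected.** For the mid-treatment visit, Research Design & Methods (Treatment period) states: "The study coordinator will use screen sharing to complete all assessment measures with the individual". For all three visits the same section adds: "All measures will be administered by a member of the study team via secure Zoom". At midpoint, Altitudes carers also "provide their perceptions of the Altitudes platform and clinical moderators via four brief questionnaires": A-HCCQ, AUQ, A-PCS and WAI-I. The Synopsis repeats these four at post-treatment.

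**Who collects them.** Under Baseline Procedures, "the study coordinator will conduct a 20- to 30-minute orientation of the Altitudes platform". Under Post-Treatment Procedures, "the study coordinator will lead Altitudes participants only through a feedback survey and individual feedback interview regarding the Altitudes platform, their online therapist, the Family" (the list goes on to name the peer support specialist and the news feed). The Treatment period text says that individual interviews "will be led by the Altitudes study coordinator and/or a graduate student in clinical psychology". Expert Moderation lists graduate students among the moderators, with family peer support workers and experienced providers.

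**Who may read the answers.** Confidentiality of Data says that the project database, including all interview transcripts, "will only be directly accessible by the research staff, clinicians and family peer support workers, involved in this project, or the principal investigator". Access to Data gives the research staff listed in the IRB application all data, but restricts moderators: "the study moderators (the online data captured within the Altitudes system").

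**What the answers feed.** Primary outcomes 1 and 2 are interview themes and counts from a 1-to-5 feedback form. Primary outcomes 3 to 6 are mean changes from mid- to post-treatment in three WAI-I scores and in perceived autonomy support. The Synopsis analyses the four questionnaires for Aim 1 with descriptive statistics.

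**The concern.** Acceptability is the primary objective, and much of the evidence for it is what carers say about a service and the people who run it. Carers who answer on a screen that staff can see, or speak to someone who introduced them to the platform or belongs to a moderating role, may soften criticism. No section provides for private entry of the ratings, requires an interviewer independent of moderation, or discusses response bias.

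The Power Analysis section says that the pilot is to inform later, adequately powered trials. If favourable ratings partly reflect the setting, the decision to proceed rests on weaker evidence than it appears to, and no analysis after the event can separate the two. Data Management also assigns all analyses to the research coordinator and a graduate student, so the same roles may both gather and code the feedback.

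The disagreement over access matters in its own right. Family peer support workers are moderators. One section opens transcripts to them and the other restricts moderators to platform data.

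**Working it through.** The plan gives no acceptability threshold, SD or expected bias, so there is no figure to reproduce. The check sets the sections side by side and adds an illustration based on assumptions.

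**Step 1: is completion private?** Screen sharing is stated for mid-treatment only. Staff administration by Zoom is stated for all visits. The section on risks for parents and caregivers says that questionnaires are sent by secure email, but not that the ratings are completed unobserved. Private completion is therefore not provided for.

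**Step 2: is the person collecting the answers independent?** The coordinator gives the orientation, then leads the feedback survey and interview. Adverse Events lists the online moderators and the research coordinator as separate sources of information, so the coordinator is not shown to be a moderator. Graduate students moderate, and a graduate student may interview. No section says that these are the same person, and none says that they must differ.

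**Step 3: which outcomes are exposed?**

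| Outcome | Type | Exposed to an upward shift? |
|---|---|---|
| Primary 1, interview themes | level | yes |
| Primary 2, feedback-form counts | level | yes |
| Aim 1 summaries of the four questionnaires | level | yes |
| Primary 3 to 6 | mid-to-post change | not necessarily |
| Site usage | passively logged | no |

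If a carer's answers are raised by b at both visits, the change is (post + b) − (mid + b) = post − mid, so a constant shift cancels. A ceiling at 5 can shrink the change. In a simulation with assumed mid-treatment mean 4.0, between-carer SD 0.75, visit SD 0.3 and true change 0.2, the mean change was 0.173 with no shift, 0.158 with b = 0.25 and 0.138 with b = 0.5. The mid-treatment mean rose from 3.959 to 4.174 and 4.369.

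**Step 4: how large could a shift be against sampling error?** The 95% half-width for one mean is t × SD/√n. The planned Altitudes group is up to 30, for which t = 2.045 (29 df). With SD 0.5 this is 2.045 × 0.5/√30 = 0.187. The SDs and shifts are assumptions.

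| SD | Half-width, n = 30 | Shift 0.25 ÷ half-width | Shift 0.5 ÷ half-width |
|---|---|---|---|
| 0.5 | 0.187 | 1.34 | 2.68 |
| 0.75 | 0.280 | 0.89 | 1.79 |
| 1.0 | 0.373 | 0.67 | 1.34 |

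With 20 carers the half-widths are 0.234, 0.351 and 0.468, and a 0.25 shift is 1.07, 0.71 and 0.53 of them. A moderate shift could match or exceed sampling error, and recruiting more carers would not remove it.

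**Step 5: can both access rules stand?** Confidentiality of Data admits clinicians and family peer support workers to all transcripts. Access to Data admits moderators to online data only. The two conflict for any moderator not on the IRB staff list. The description of the Community calls peer workers investigational staff, so some may be on that list, but the documents do not say.

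**The case against.** The strongest reply is that staff-guided completion is a reasonable choice in a pilot without power calculations, since it helps completeness. The person sharing the screen is the coordinator, who is not described as one of the moderators being rated. Coordinator-led interviewing is what Post-Treatment Procedures already describes, and overlap between student moderators and student interviewers is only possible. These points stand, and they limit the finding to a risk.

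Four stronger readings are tempting, and the documents do not support them:

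- **Acceptability is biased upward.** Nothing in the documents shows that bias occurs or how large it is.
- **The comparison with controls is distorted.** One could set an assumed shift in one group against the two-group half-width of 1.96 × √(2/30) = 0.51 SD. That figure does not bear on the primary outcomes, which apply to the Altitudes group only. The coordinator sees both groups for the common battery, which does not rate staff. Unequal bias is conjecture.
- **The rated staff will read what was said about them, and this shapes answers.** The access rules conflict, the Treatment period text says that feedback sessions are de-identified, and later access affects answers only if carers know or suspect it. De-identification is limited protection with at most 30 carers from two clinics, but that does not establish the effect.
- **Staff administration contradicts the scales' self-report labels.** A self-report scale can be completed with staff present.

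**Conclusion.** The concern holds as an unmitigated risk of social-desirability bias, of unknown size, in primary outcomes 1 and 2 and in the Aim 1 summaries of rating levels. It does not necessarily reach primary outcomes 3 to 6, where a shift equal at both visits cancels and a ceiling would shrink the change. Passively logged usage is unaffected, and no effect on the between-group comparison is shown.

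The ratios of 0.67 to 1.34 for a 0.25-point shift rest on assumed SDs of 0.5 to 1.0, 30 carers and a shift chosen for illustration. They show that such a bias could matter, not that it is present. The difference between Confidentiality of Data and Access to Data is a separate drafting conflict that needs resolving whatever the size of any bias. Overall this is an inexpensive improvement, not a flaw that undermines the study.

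**What to change.** 1. Have carers enter the four platform and moderator questionnaires and the feedback form themselves through an individual survey link, for example in REDCap, without screen sharing. Staff stay on the call to answer questions, which should protect completeness.
2. State that nobody who has moderated a carer interviews that carer. The coordinator can meet this rule if, as the text suggests, the coordinator does not moderate.
3. Reconcile Confidentiality of Data with Access to Data on who may open ratings and transcripts, preferably excluding the staff being rated. The documents do not show which rule was intended, so the investigators must decide.

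Cost: no extra staff are needed. REDCap is already in use, but the plan describes it for data entry and management, not for participant links, so some set-up is required. Some carers may need help with the link.
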